6.2.2 Enrollment, Baseline, and/or Randomization

Enrollment

Subjects are considered enrolled once the informed consent document has been signed and randomization has occurred. Only one written informed consent document will be used, as we have

requested a partial HIPAA waiver for screening.

Baseline Assessments

- Pre-Treatment Pain Intensity Assessment (Pre) using a 0-10 NRS^{58,59} will be collected: a) for acupuncture patients, before administration of acupuncture; b) for usual care patients who receive a pain medication order within 60 minutes (+/- 15 minutes) of being roomed, just before or at administration of pain medication; or c) for usual care patients who have not received a medication order within 60 minutes (+/- 15 minutes) of being roomed, at 60 minutes (+/- 15 minutes). The collection time window of 60 minutes was based on median time from being roomed to first pain medication (54 minutes) using data obtained from the ANW ED pilot study (See Figure 1). Pre-treatment pain assessments will be timed to be completed immediately prior to the administration of either the acupuncture or usual care treatments.
- Anxiety scores using a 0-10 NRS^{58,59}
- Expectancy will be measured with the following questions.
 - By the end of the treatment period in the ER, how much improvement in your pain symptoms do you think will occur?
0% 10% 20% 30% 40% 50% 60% 70% 80% 90% 100%

Now, please close your eyes for a few moments and try to identify what you really feel about the treatment and its likely success. Then answer the following questions:

- At this point, how much do you really feel that the treatment will help you to reduce your pain symptoms?
1 2 3 4 5 6 7 8 9
Not at all Somewhat Very much
- By the end of your treatment period in the ER, how much improvement in your pain symptoms do you really feel will occur?
0% 10% 20% 30% 40% 50% 60% 70% 80% 90% 100%

Randomization

Immediately after screening, obtaining informed consent from eligible patients, and collecting baseline data, the study staff will randomize patients to either Acupuncture or Usual Care.

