 - 1. Several times a day
 - 2. Once a day
 - 3. Several times a week
 - 4. Once a week
 - 5. Several times per month
 - 6. Once per month
 - 7. Can't recall
 - 8. Decline to answer
 - 9. Other: [FREE TEXT]

5. Have you visited an emergency room for pain within the past 12 months?

- a. Yes
- b. No
- c. Do not know
- d. Decline to answer
 - i. If yes, how many times in the last year?
 - 1. 1

- 2. 2-4
- 3. 5-7
- 4. 11+
- 5. Decline to answer

6. Have you used any non-medication treatments for your pain?

- a. Yes
- b. No
- c. Don't know
- d. Decline to answer
 - i. If yes, what methods have you used? Please select all that apply.
 - 1. Physical Therapy
 - 2. Chiropractor
 - 3. Massage
 - 4. Exercise
 - 5. Acupuncture
 - 6. Hot / cold therapy
 - 7. Meditation
 - 8. Decline to answer
 - 9. OTHER [FREE TEXT]

7. Have you ever received acupuncture?

- a. Yes
- b. No
- c. I don't know
 - i. If yes, was the acupuncture effective to relieve your symptoms?
 - 1. Yes
 - 2. No
 - 3. Do not know
 - 4. Decline to answer

8. Please rate your confidence that non-medication treatments can reduce pain, on a 0-10 scale, where 0 is not confident and 10 is completely confident.

0 1 2 3 4 5 6 7 8 9 10 Unsure

“PRE” FORM – Patient facing, same for both arms, blinded to coordinator

INSTRUCTIONS: “There are some additional questions for you to answer on this iPad or your phone. I will be here to answer any questions you may have. Please do not show me the answers to these questions. Please hand the iPad back to me when you are done or let me know when you have completed the survey on your phone.”

SECTION 1 – Demographics Patient Facing, to be answered by the patient; blinded. Questions need to be presented as shown here in longitudinal fashion.

1. What is your date of birth?
2. What is your ethnicity?
 - a. Hispanic or Latinx
 - b. Not Hispanic or Latinx
 - c. Decline to answer
3. What is your race? Check all that apply.
 - a. American Indian or Alaska Native
 - b. Asian
 - c. Black or African American
 - d. Native Hawaiian or other Pacific Islander
 - e. White
 - f. Other [FREE TEXT]
 - g. Decline to answer
4. My sex assigned at birth is:
 - a. Female
 - b. Male
 - c. Intersex
 - d. Decline to answer
5. What is your current gender identity?
 - a. Male
 - b. Female
 - c. Trans male/Trans man
 - d. Trans female/Trans woman
 - e. Genderqueer/Gender non-conforming
 - f. Different Identity [FREE TEXT]
 - g. Decline to answer
6. How much formal education do you have?

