 - a. No high school diploma
 - b. High school or equivalent
 - c. Education beyond high school, but have not completed a bachelor's degree
 - d. College degree
 - e. Graduate or professional degree
 - f. Decline to answer
7. What is your current marital status?
 - a. Married, spouse in household

- b. Married, spouse not in household
- c. Significant other or partner
- d. Widowed
- e. Divorced
- f. Separated
- g. Never married
- h. Decline to answer

8. What is your current employment status?

- a. Working full-time
- b. Working part-time
- c. Not employed due to other responsibilities (raising children, keeping house, student)
- d. Retired
- e. On medical leave or disabled
- f. Unemployed, looking for work
- g. Other [FREE TEXT]
- h. Decline to answer

9. What is the annual income of your household?

- a. Less than \$20,000
- b. \$20,000 to \$50,000
- c. \$50,001 to \$100,000
- d. \$100,001 to \$150,000
- e. More than \$150,000
- f. Decline to answer

10. Which of the following is your primary health insurance?

- a. Medicare
- b. Medicaid
- c. Other insurance
- d. No insurance
- e. Decline to answer

11. Approximately how much do you weight (in pounds)? [FREE TEXT]

12. What is your approximate height?

- a. Feet
 - i. 3
 - ii. 4
 - iii. 5
 - iv. 6
 - v. 7

- b. Inches
 - i. 0
 - ii. 1
 - iii. 2
 - iv. 3
 - v. 4
 - vi. 5
 - vii. 6
 - viii. 7
 - ix. 8
 - x. 9
 - xi. 10
 - xii. 11

SECTION 2 – Expectancy Questions Patient Facing, to be answered by the patient; blinded. Questions need to be presented as shown here in longitudinal fashion.

1. By the end of the treatment period in the ER, how much improvement in your pain symptoms do you **think** will occur?
 0% 10% 20% 30% 40% 50% 60% 70% 80% 90% 100% Unsure

Now, please close your eyes for a few moments and try to identify what you really **feel** about the treatment and its likely success. Then answer the following questions:

2. At this point, how much do you really feel that the treatment will help you to reduce your pain symptoms?

1	2	3	4	5	6	7	8	9
Not at all				Somewhat				Very much
								Unsure

3. By the end of your treatment period in the ER, how much improvement in your pain symptoms do you really **feel** will occur?
 0% 10% 20% 30% 40% 50% 60% 70% 80% 90% 100% Unsure

SECTION 3 – Pain

1. Please rate your pain, **right now**, on a scale of 0 to 10, where 0 is no pain, and 10 is the worst pain imaginable.

0	1	2	3	4	5	6	7	8	9	10
---	---	---	---	---	---	---	---	---	---	----

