SECTION 4 – Anxiety

2. Please rate your anxiety, **right now**, on a scale of 0 to 10, where 0 is no anxiety, and 10 is the worst anxiety imaginable.

0	1	2	3	4	5	6	7	8	9	10
---	---	---	---	---	---	---	---	---	---	----

SECTION 5 – Randomization (logic to open up this form)

→ Build randomization module into REDCap

POST ACUPUNCTURE FORM – Patient facing, blinded to coordinator

INSTRUCTIONS: “There are some additional questions for you to answer on this iPad or your phone. I will be here to answer any questions you may have. Please do not show me the answers to these questions. Please hand the iPad back to me when you are done or let me know when you have completed the survey on your phone.”

SECTION 1 – Pain

1. Please rate your pain, **right now**, on a scale of 0 to 10, where 0 is no pain, and 10 is the worst pain imaginable.

0 1 2 3 4 5 6 7 8 9 10

SECTION 2 – Anxiety

2. Please rate your anxiety, **right now**, on a scale of 0 to 10, where 0 is no anxiety, and 10 is the worst anxiety imaginable.

0 1 2 3 4 5 6 7 8 9 10

SECTION 3 – Satisfaction

3. How satisfied are you with how your pain was managed during your ED visit?

- a. Very Unsatisfied
- b. Somewhat Unsatisfied
- c. Neutral
- d. Somewhat Satisfied
- e. Very Satisfied

4. Overall how satisfied are you with your treatment during your ED visit?

- a. Very Unsatisfied
- b. Somewhat Unsatisfied
- c. Neutral
- d. Somewhat Satisfied
- e. Very Satisfied

SECTION 4 – ED Impact (Acupuncture Arm Only)

1. Please rate the impact of acupuncture on your ED visit today.

- a. Very Negative
- b. Somewhat Negative
- c. Neutral
- d. Somewhat Positive
- e. Very Positive

POST ACUPUNCTURE FORM – Coordinator facing, information gathered from Acupuncturist

SECTION 4 – Ear Seeds (Acupuncture Arm Only)

1. Did the participant receive ear seeds in the ER
 - a. Yes
 - b. No

POST USUAL CARE FORM – Patient facing, blinded to coordinator

INSTRUCTIONS: “There are some additional questions for you to answer on this iPad or your phone. I will be here to answer any questions you may have. Please do not show me the answers to these questions. Please hand the iPad back to me when you are done or let me know when you have completed the survey on your phone.”

SECTION 1 – Pain

1. Please rate your pain, **right now**, on a scale of 0 to 10, where 0 is no pain, and 10 is the worst pain imaginable.

0 1 2 3 4 5 6 7 8 9 10

SECTION 2 – Anxiety

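### The baseline ED-visit item has no answer for 8 to 10 visits and counts fewer kinds of visit than Section 6.1 lists; secondarily, the expectancy items are not treatment-specific

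*Combined protocol and SAP*

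**What the plan says.** **ED visits.** The Section 6.1 schedule lists ED visits in the last year among the baseline variables of interest, without restricting the reason for the visit. The matching question is item 5 of the Baseline form in Appendix B, which study staff ask and enter. It first asks whether the patient went to an emergency room for pain in the past 12 months. A yes opens the count item, "If yes, how many times in the last year", with five numbered answers: 1, 2-4, 5-7, 11+ and decline.

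**Expectancy.** Section 6.2.2 places three expectancy questions under Baseline Assessments and puts randomisation afterwards: "collecting baseline data, the study staff will randomize patients to either Acupuncture or Usual Care". In Appendix B they form Section 2 of the PRE form, headed "FORM – Patient facing, same for both arms, blinded to coordinator". Randomisation comes later on the same form: "SECTION 5 – Randomization (logic to open up this form". Items 1 and 3 ask about improvement over the ER episode; item 1 begins "By the end of the treatment period in the ER, how much improvement in your pain symptoms do you". Before item 2, patients are asked to consider what they feel "about the treatment and its likely success. Then answer the following questions". Item 2 then asks "At this point, how much do you really feel that the treatment will help you to reduce your pain symptoms". All three items offer an unsure option, and no later form repeats them.

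**The concern.** A closed count item should give every patient exactly one correct answer. This one leaves a hole in the upper range, among frequent ED users. It also counts a narrower set of visits than the schedule lists, so the recorded variable and the listed variable differ even where the categories work.

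Expectancy raises a question of what is being measured. The trial is un-blinded, compares acupuncture with usual care rather than sham, and collects self-rated pain. Expectation of acupuncture in particular is therefore worth describing. A patient who has just consented to a two-arm study and does not know the allocation could take *the treatment* in item 2 to mean acupuncture, ED medication or the whole visit.

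The primary objective is to refine procedures for a definitive trial, and Section 9.5.1 says the forms will be evaluated for quality and completeness. Form defects are therefore within what this study sets out to find.

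**Working it through.** The plan states no figure on this point, so there is none to reproduce.

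**1. Coverage of the count item.** The answers cover {1}, {2, 3, 4}, {5, 6, 7} and {11, 12, ...}. A patient with no visit for pain answers no to the opening question. Checking counts 1 to 20, the uncovered ones are 8, 9 and 10 and no others. With an 8-10 answer added, none is uncovered. The answers are numbered 1 to 5 without a break, so nothing suggests a line lost when the text was read from the PDF.

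**2. Definition.** Section 6.1 lists ED visits in the last year. Item 5 admits only visits for pain. A patient with several ED visits, none for pain, answers no and is never asked for a count.

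**3. Possible size of the gap.** The documents give no distribution of visit counts, so the share p of patients with 8 to 10 visits is an assumption. With n = 150 (Section 9.2), the expected number affected is 150 × p, and the chance of at least one is 1 − (1 − p)^150.

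| Assumed p | Expected patients | Chance of at least one |
|---|---|---|
| 0.5% | 0.75 | 53% |
| 1% | 1.5 | 78% |
| 2% | 3 | 95% |
| 5% | 7.5 | over 99.9% |
| 10% | 15 | over 99.9% |

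For example, at p = 1%: 150 × 0.01 = 1.5, and 1 − 0.99^150 = 0.78.

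**4. Expectancy: order and referent.** The PRE form runs demographics, expectancy, pain, anxiety, randomisation, in Sections 1 to 5. Section 6.2.2 gives the same order: randomisation follows "Immediately after screening, obtaining informed consent from eligible patients, and collecting baseline data". By both, patients answer before allocation, and the wording is identical for everyone. Item 2 and its lead-in name no treatment. Items 1 and 3 name no therapy either, but they are anchored to the ER treatment period and make sense as expectation of the ER episode in either arm. The undefined referent is thus confined to item 2 and its lead-in, and none of the three items isolates acupuncture. The wording applies to all 150 records, and to the 15 pilot patients taken through the same protocol.

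**The case against.** **Expectancy is still usable.** A score taken before randomisation cannot be affected by allocation and is a legitimate baseline covariate. Baseline item 7 records previous acupuncture and whether it helped, and item 8 records confidence in non-medication treatments on a 0-10 scale. This largely stands. A reader might infer that the expectancy data are uninterpretable; the documents do not support that. They support only that the scores are not treatment-specific. Items 7 and 8 cover related beliefs but do not replace a named acupuncture question.

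**No planned analysis depends on either variable.** The primary outcomes concern recruitment, retention and data completeness. Section 9.5 plans descriptive statistics for pain change, and the Mann-Whitney test in Section 9.2 belongs to the future trial. This stands. A reader might want expectancy as a covariate in a comparison of Post pain, but Section 9 specifies no such between-arm comparison for this trial.

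**The ED-visit gap does not bear on reach.** A reader might infer that it hides whether frequent users were recruited. The Baseline form is completed only after consent, so it cannot show who among the eligible took part. Section 9.5.1 uses demographics and presenting complaint for that.

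**The dilution of expectancy cannot be bounded as one might expect.** A reader might suppose that if half the patients think of each treatment, the score keeps at most half its correlation with acupuncture expectancy. Under a random 50/50 split with equal means and SDs, that correlation is 0.5(1 + r), where r is the correlation between the two expectancies. This gives 0.5 at r = 0 and 0.75 at r = 0.5, so half is a floor for r ≥ 0. The documents give neither the split nor r.

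**Staff may pick a neighbouring category.** Patients with 8 to 10 visits need not be lost altogether. That is true, but a neighbouring category is a wrong one.

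**Conclusion.** The ED-visit item is wrong as written. Anyone with 8, 9 or 10 visits is misclassified, recorded as declining or left blank; counts of 1 to 7 and of 11 or more are classified correctly. The restriction to visits for pain does not match Section 6.1. The number affected cannot be determined from the documents, and the figures above rest on an assumed share.

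The expectancy point is secondary. By form order and by the randomisation step in Section 6.2.2, the items precede allocation, and they measure general expectation of ER care rather than expectancy of acupuncture. One caveat applies: Section 6.2.2 also times the Pre pain score differently by arm, which presupposes a known allocation, although that score sits on the same PRE form ahead of randomisation. Those passages need to be reconciled. Section 6.1 also lists expectancy under other variables of interest, whereas Section 6.2.2 treats it as a baseline assessment.

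Both matters are minor. They affect descriptive data and the instruments carried to the definitive trial, not the recruitment or retention estimates.

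**What to change.** 1. In Baseline item 5, add an 8-10 answer, or record the count as a number. Adding the answer closes the gap and keeps the existing detail. Cost: one changed option in REDCap.
2. Make item 5 and the Section 6.1 variable agree: either all ED visits in the last year or those for pain, with the same wording in both places. Cost: one line of text.
3. As a cheap improvement for the definitive trial, keep expectancy before randomisation but name the treatment in item 2. Ask it once for assignment to acupuncture and once for assignment to usual ED care, adjust the lead-in to match, and report both descriptively by arm. Cost: one extra tablet item and a slightly longer PRE form.
4. State when the PRE form is completed relative to randomisation, so that the form order and the arm-dependent timing of the Pre score in Section 6.2.2 agree.

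If records already exist under the present item 5, report that 8 to 10 visits had no answer and that only visits for pain were counted.

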6. STUDY PROCEDURES

6.1 Schedule of Evaluations

Randomized Control Trial

Treatment Variables. Main patient reported treatment outcomes (PROs) include pain intensity and anxiety. The use of self-reported pain ratings to assess pain is standard clinical practice.^{68,69} Although self-report of pain intensity is subjective, a reliable physiological measure to quantify pain has not been identified.⁷⁰ These measures will be collected via tablet computer in the PHI-approved data collection tool (REDCap). A similar process was used in [name]'s pilot RCT. The study staff will hand the patient a tablet for confidential self-administration. Once the patient completes the questionnaires, the answers will be masked so the research staff will not have access to the scores. To keep research staff blinded to scores, the data collection tool will be designed so that the study staff will only be able to determine that valid pain and anxiety scores were entered by the patient. In other words, staff will not have access to the actual pain or anxiety scores until the statistician conducts the final analysis. Data will be collected as shown in Table below.

Treatment Variables	Measure/Source	Data Collection Time point			
		Pre-Treatment	Post-Treatment	ED Discharge	1-week and 4-week Follow-up
Primary Assessment (* and bold)					
Pain Intensity	Numeric Rating Scale, 0-10^{58,59}	X	X*	X*	X^
Anxiety	Numeric Rating Scale, 0-10^{58,59}	X	X*	X*	X^
Secondary Assessment (^ and italic)					
All pain medications in the ED	EHR			X^	
Pain medication/opioid use	Self-report				X^
Baseline variables of interest					
Demographics	EHR data and self-report	X			
Current Medications		X			
Opioid use – last 30 days	Self-report	X			
Previous acupuncture use		X			

ED visits in last year	X
Other variables of interest	
Expectancy	Self-report
Satisfaction questions	X
ED impact (ACUPUNCTURE ONLY)	X

Qualitative Interviews

Patient Interview Guide

U01 Acupuncture Study Patient Interview Topic Guide Preliminary Draft 10-23-20
1. Pain narrative—history, cause, impact, course, treatment experiences Possible prompts: i. Tell me about your pain condition... ii. How long have you had it? iii. What causes it? iv. How does it impact you? v. Tell me about your pain condition over time—wax/wane? Always the same? Exacerbating issues? vi. Tell me about your treatment and management experiences

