1 week follow-up Assessment (Follow-up) will be obtained via REDCap based text message or email (or phone call from research staff) at 1 week (+/- 4 days) of patient's ED discharge for both arms. To maintain assessor blinding, any 1-week phone calls (if needed) will be conducted by a research staff (SC or RA) who did not interact with the patient during their study participation in the ED.

- Pain Assessment (Post) using a 0-10 NRS
- Anxiety scores using a 0-10 NRS
- Satisfaction and will be measured through brief questions. All participants will be asked to answer;
 - “How satisfied are you with how your pain was managed during your ED visit” on the 5-point Likert scale.
 - “Overall how satisfied are you with your treatment during your ED visit?” on the same Likert Scale.
- Pain medications utilized from ED discharge to 1 week after discharge will be obtained from patients via phone call, email, or text messaging via the secure REDCap electronic data collection tool.

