2. Please rate your anxiety, **right now**, on a scale of 0 to 10, where 0 is no anxiety, and 10 is the worst anxiety imaginable.

0 1 2 3 4 5 6 7 8 9 10

SECTION 3 – Satisfaction

3. How satisfied are you with how your pain was managed during your ED visit?

- a. Very Unsatisfied
- b. Somewhat Unsatisfied
- c. Neutral
- d. Somewhat Satisfied
- e. Very Satisfied

4. Overall how satisfied are you with your treatment during your ED visit?

- a. Very Unsatisfied
- b. Somewhat Unsatisfied
- c. Neutral
- d. Somewhat Satisfied
- e. Very Satisfied

FOLLOW UP FORM for 1 week F/U AND 4 week F/U – To be completed by everyone, ideally from an automatic text and email generated by REDCap. If not by email, coordinator will text or phone the participant and enter the answers into REDCap.

Instructions: Below are some questions that ask you to remember what happened since your discharge from the Emergency Room on [er_visit_date].

Section 1-Medications

1. Since your discharge from the Emergency Room on [er_visit_date], have you taken any pain medications for your medical condition?
 - a. Yes
 - b. No
 - c. I don't know
 - i. If yes, “were these medications prescribed by a medical professional?

Check all that apply:

1. Yes, by Emergency room provider

2. Yes, by Primary Care Provider
 3. Yes, by Other medical professional [FREE TEXT]
 4. No
 5. I don't know
2. [branched from 1.a.i.1] Since your discharge, which pain medication(s) was prescribed by your EMERGENCY ROOM PROVIDER? Please select all that apply. (radio):
 1. Oxycodone (OxyContin, Oxecta, Roxicodone)
 2. Oxycodone / Acetaminophen (Percocet, Endocet, Roxicet)
 3. Oxycodone and Naloxone (Targiniq ER)
 4. Fentanyl (Actiq, Duragesic, Fentora)
 5. Methadone (Dolophine, Methadose)
 6. Morphine (Astramorph, Avinza, Kadian, MS Contin, Ora-Morth SR)
 7. Codeine
 8. Tylenol with codeine
 9. Hydrocodone (Hysingla ER, Zohydro ER)
 10. Hydrocodone / Acetaminophen (Lorcet, Lortab, Norco, Vicodin)
 11. Hydromorphone (Dilaudid, Exalgo)
 12. Aspirin
 13. Tylenol
 14. Ibuprofen
 15. Naproxen
 16. Celebrex
 17. Other: [FREE TEXT]
 18. Do not know
 19. Decline to answer
- a. How often have you taken these pain medication(s) on average?
 1. Several times a day
 2. Once a day
 3. Several times a week
 4. Once a week
 5. Several times per month
 6. Once per month
 7. Can't recall
 8. Decline to answer
 9. Other: [FREE TEXT]

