3. [branched from 1.a.i.2] Since your discharge, which pain medication(s) was prescribed by your PRIMARY CARE PROVIDER? Please select all that apply. (radio):
 1. Oxycodone (OxyContin, Oxecta, Roxicodone)
 2. Oxycodone / Acetaminophen (Percocet, Endocet, Roxicet)
 3. Oxycodone and Naloxone (Targiniq ER)

4. Fentanyl (Actiq, Duragesic, Fentora)
5. Methadone (Dolophine, Methadose)
6. Morphine (Astramorph, Avinza, Kadian, MS Contin, Ora-Morth SR)
7. Codeine
8. Tylenol with codeine
9. Hydrocodone (Hysingla ER, Zohydro ER)
10. Hydrocodone / Acetaminophen (Lorcet, Lortab, Norco, Vicodin)
11. Hydromorphone (Dilaudid, Exalgo)
12. Aspirin
13. Tylenol
14. Ibuprofen
15. Naproxen
16. Celebrex
17. Other: [FREE TEXT]
18. Do not know
19. Decline to answer

- a. How often have you taken these pain medication(s) on average?
 1. Several times a day
 2. Once a day
 3. Several times a week
 4. Once a week
 5. Several times per month
 6. Once per month
 7. Can't recall
 8. Decline to answer
 9. Other: [FREE TEXT]
4. [branched from 1.a.i.3] Since your discharge, which pain medication(s) was prescribed by ANOTHER MEDICAL PROFESSIONAL? Please select all that apply. (radio)
 1. Oxycodone (OxyContin, Oxecta, Roxicodone)
 2. Oxycodone / Acetaminophen (Percocet, Endocet, Roxicet)
 3. Oxycodone and Naloxone (Targiniq ER)
 4. Fentanyl (Actiq, Duragesic, Fentora)
 5. Methadone (Dolophine, Methadose)
 6. Morphine (Astramorph, Avinza, Kadian, MS Contin, Ora-Morth SR)
 7. Codeine
 8. Tylenol with codeine
 9. Hydrocodone (Hysingla ER, Zohydro ER)
 10. Hydrocodone / Acetaminophen (Lorcet, Lortab, Norco, Vicodin)
 11. Hydromorphone (Dilaudid, Exalgo)

12. Aspirin
13. Tylenol
14. Ibuprofen
15. Naproxen
16. Celebrex
17. Other: [FREE TEXT]
18. Do not know
19. Decline to answer

a. How often have you taken these pain medication(s) on average?

1. Several times a day
2. Once a day
3. Several times a week
4. Once a week
5. Several times per month
6. Once per month
7. Can't recall
8. Decline to answer
9. Other: [FREE TEXT]

5. [branched from 1.a.i.4] Since your discharge from the emergency room on [er_visit_date], which pain medication(s) have you taken (not prescribed by your emergency room provider, primary care provider or other medical professional)? Please select all that apply

1. Oxycodone (OxyContin, Oxecta, Roxicodone)
2. Oxycodone / Acetaminophen (Percocet, Endocet, Roxicet)
3. Oxycodone and Naloxone (Targiniq ER)
4. Fentanyl (Actiq, Duragesic, Fentora)
5. Methadone (Dolophine, Methadose)

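### The 1-week and 4-week form opens no drug list for a patient who took pain medication but ticks only that the prescriber is unknown, so self-reported opioid use cannot be derived from that form

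*Combined protocol and SAP*

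**What the plan says.** The table in section 6.1 (Schedule of Evaluations) lists "Pain medication/opioid use" by self-report at 1 and 4 weeks as a secondary assessment. Section 6.2.4 names the source: "Pain medications utilized from ED discharge to 1 week after discharge will be obtained from patients". Section 6.2.5 says the same for the period up to 4 weeks.

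The instrument is the Appendix B follow-up form, Section 1 (Medications), which serves both time points. Item 1 asks whether, since discharge, "have you taken any pain medications for your medical condition". A yes leads to "were these medications prescribed by a medical professional", marked "Check all that apply". The five answers are the ER provider, the primary care provider, another professional, no, and don't know. The later items carry their own branching labels:

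- Item 2: "branched from 1.a.i.1] Since your discharge, which pain medication(s) was prescribed by your EMERGENCY ROOM PROVIDER"
- Item 3: "branched from 1.a.i.2] Since your discharge, which pain medication(s) was prescribed by your PRIMARY CARE PROVIDER"
- Item 4: branched from 1.a.i.3, for drugs from another professional
- Item 5: "branched from 1.a.i.4] Since your discharge from the emergency room on [er_visit_date], which pain medication(s) have you taken", restricted to drugs that no professional prescribed

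Each of these items has a drug list and a frequency question. The next printed item is numbered 9 and concerns non-drug methods.

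**The concern.** The form treats not knowing the prescriber as a reason not to ask about the drug. These are different kinds of ignorance, and the form recognises this elsewhere: each drug list has its own option for a patient who cannot name the drug. The baseline form also asks for drug names without first asking who prescribed them, so a patient could have named drugs at baseline and none at follow-up.

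Three stated purposes are touched. Opioid use at follow-up is among the evidence gaps that section 2.1 says this study will fill. Data completeness is part of the feasibility outcome in section 9.5.1, and here the instrument itself would create the missing values. The primary objective (section 1.1) is to refine procedures for a larger trial, so an uncorrected form could carry the gap forward.

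**Working it through.** **Step 1. Match each prescriber answer to a drug list (Appendix B, follow-up form, Section 1).**

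| Answer to the prescriber question | Item that opens | Drug and frequency recorded |
|---|---|---|
| 1.a.i.1 ER provider | 2 | yes |
| 1.a.i.2 primary care provider | 3 | yes |
| 1.a.i.3 other professional | 4 | yes |
| 1.a.i.4 no | 5 | yes |
| 1.a.i.5 don't know | none printed | no |

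Four of the five answers reach a drug list.

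**Step 2. Separate the two cases that multiple ticking allows.**

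- Only 1.a.i.5 ticked: the form holds a yes for pain medication, with no drug and no frequency. Opioid use is undetermined.
- 1.a.i.5 ticked with another answer: the list for the other answer opens. Only a drug of unknown origin is missed, if there is one. If the listed drug is an opioid, opioid use is already established.

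**Step 3. Look for another source.**

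- Section 10.2: the EHR extract covers pain medication in the ED and opioid prescriptions at discharge. It shows prescribing, not use, and misses other prescribers and non-prescribed drugs.
- The week-4 form asks about the whole period since discharge, so it may partly fill a week-1 gap. The plan does not say that it will be used in this way, and nothing later fills a week-4 gap.
- The form is meant to be completed mainly from an automatic message, and no instruction to probe this answer is given for phone contacts.

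**Step 4. Size.** The plan has no figure to reproduce. Inputs:

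- Enrolment N = 150 (section 9.2).
- Response r = 16/46 = 0.35, the pilot's 30-day follow-up (section 2.2).
- Share of responders taking a pain drug, u = 0.60 to 0.80 (assumption).
- Share of those ticking only 1.a.i.5, k = 0.03 to 0.10 (assumption).

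Affected per time point = N × r × u × k:

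- Low: 150 × 0.35 × 0.60 × 0.03 = 0.9
- High: 150 × 0.35 × 0.80 × 0.10 = 4.2

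That is about 1 to 4 patients. The count scales with response. At complete follow-up (r = 1) it would be 150 × 0.60 × 0.03 = 2.7 to 150 × 0.80 × 0.10 = 12.

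**Step 5. Effect on an arm's opioid proportion.** With about 75 per arm and complete follow-up, each undetermined patient widens the worst-case bounds by 1/75 = 1.3 percentage points. At 35% response an arm has 75 × 0.35 = 26.25 responders, and each such patient widens the bounds among responders by 1/26.25 = 3.8 points.

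**The case against.** The best case against making much of this has four parts.

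**The printed form may be incomplete.** Item numbers jump from 5 to 9, and Appendix B reads in part as build instructions. An item for 1.a.i.5 may have been deleted, or may exist in the live system. This stands as a reason to check the build first. The printed text shows no such item.

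**The answer may be rare.** Non-prescribed drugs belong under the no answer, which has a list. The don't-know answer is needed only when the origin is truly unclear, and nothing in the documents suggests that this is common. This stands, and it is why the size rests on assumptions. A reader might put the pilot's 78% into the formula and get 150 × 0.78 × 0.80 × 0.10 = 9.4 patients. The documents do not support that as a follow-up figure: it is the pilot's rate for post-treatment and discharge scores collected in the ED.

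**The consequence is small.** The primary outcomes are recruitment and retention (section 3). Section 9 defines no opioid-use variable and no between-arm test of one. This stands and limits the severity.

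**The gap would be visible.** A reader might infer that these patients will be counted as non-opioid, or that their opioid status is lost altogether. Neither follows. No section gives such a coding rule, a yes with no drug is plainly incomplete, and sections 9.5 and 9.6 commit to examining the reasons for missing values. The EHR extract also keeps opioid prescriptions at discharge. Examining a gap does not recover the drug name, however, and the EHR does not show use.

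**Conclusion.** The point holds for the form as printed, at minor severity. A patient who reports taking pain medication and ticks only 1.a.i.5 leaves a record from which self-reported opioid use cannot be derived at that time point. A patient who ticks 1.a.i.5 together with another answer loses at most the drugs of unknown origin.

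The likely size is about 1 to 4 patients per time point at the pilot's 30-day response, and more if the new follow-up methods raise response. That range depends on the two assumed shares (60-80% and 3-10%), for which the documents offer no evidence. The branching gap itself does not depend on them. It depends only on the live build matching Appendix B.

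A patient who answers don't know to item 1 itself also sees no drug list, but is not a confirmed user and falls outside this point.

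**What to change.** 1. Compare the live REDCap build with Appendix B, and explain or correct the jump from item 5 to item 9.
2. If no item covers 1.a.i.5, add a drug list and frequency question branched from it, with a stem such as: which pain medication(s) have you taken where you are not sure who prescribed them?
3. Keep item 5 for non-prescribed drugs. Opening item 5 to both answers would merge two groups that the form separates, and a patient who ticked both could not be resolved.
4. State that self-reported opioid use is derived from all five lists.
5. For data already collected, report patients who ticked only 1.a.i.5 in their own category, user with drug unknown, and not as non-opioid. If the week-4 answer or the EHR discharge prescription is used as supporting information, say so.

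The cost is one branching rule and one extra item, seen only by the few patients who tick this answer. Some of them may still be unable to name the drug, so recovery may not be complete.
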